4.2.3.5. Subgroup Analysis

Forest plots will be provided displaying analysis results for each subgroup listed in Section 2.5. The point estimate of the treatment difference and its 90% confidence interval for each subgroup will be based on an MMRM analysis for the primary endpoint using the appropriate contrast. The model will include baseline MADRS total score as a covariate, and treatment, day, subgroup, day-by-treatment interaction and treatment-by-subgroup as fixed effects. The terms in the model will be adjusted for the subgroup of baseline MADRS total score (\leq / $>$ median). Baseline MADRS total score (as a continuous covariate) will not be included in the model when the dichotomized baseline MADRS total score is included in the model.

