As noted above, Study ESKETINTRD2003 is a 2-panel, doubly-randomized, double-blind, placebo-controlled, multicenter study.¹⁶ Panel A was conducted in the US and Belgium and Panel B in Japan. Panel A assessed the efficacy and safety of 3 dose strengths of intranasal esketamine (28, 56, and 84 mg) administered twice a week in subjects with TRD. Panel B is designed to assess the efficacy and safety of 14-mg and 56-mg dose strengths. In Panel A, subjects in Period 1 (1-week duration) were randomly assigned in a 3:1:1:1 ratio to placebo (33 subjects), esketamine 28 mg (11 subjects), esketamine 56 mg (11 subjects), or esketamine 84 mg (12 subjects). An initial analysis of the data from the double-blind phase of Panel A indicates that of the 67 subjects randomized in Period 1, 63 entered Period 2 (1-week duration), in which 28 placebo subjects who were eligible for re-randomization at the end of Period 1, were randomly assigned in a 1:1:1:1 ratio to placebo (n=6), esketamine 28 mg (n=8), esketamine 56 mg (n=9), or esketamine 84 mg (n=5). Subjects eligible for re-randomization had to have a Quick Inventory of Depressive Symptomatology - Self Report (QIDS-SR₁₆) total score of >11 at the end of Period 1.¹⁶

In Panel A, the improvement (with respect to change in MADRS total score from baseline [Day 1] to Day 8) in all 3 esketamine dose groups reached statistical significance (p=0.021, p=0.001, and p<0.001 for esketamine 28, 56, and 84 mg, respectively) compared with placebo. The results of the 2 periods were consistent. The mean differences from placebo on Day 8 (after 1 week of treatment), estimated using data from the combined periods, were:

- Esketamine 28 mg: -4.2 (standard error [SE] 2.09);
- Esketamine 56 mg: -6.3 (SE 2.07);
- Esketamine 84 mg: -9.0 (SE 2.13).

The effect sizes (confidence interval [CI]) in Period 1 for esketamine, compared with placebo, were:

- Esketamine 28 mg: 0.43 (-0.259-1.118);
- Esketamine 56 mg: 0.92 (0.201-1.621);
- Esketamine 84 mg: 1.19 (0.473-1.883).

The duration of effect with the 28-mg dose appears to be shorter, with the MADRS total score higher on Day 8 than on Day 2. The duration of effect for the 56- and 84-mg doses appears to support twice-a-week dosing.¹⁶

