11.2. Sample Size Determination

The sample size for this study was calculated assuming a treatment difference for the double-blind induction phase of 4, 4.5, 5 points in MADRS total score between each dose (28 mg, 56 mg, 84 mg) of esketamine and the placebo respectively, a SD of 10 for each treatment group, a 1-sided significance level of 0.05 and a drop-out rate of 12.5%. A total of 183 subjects will need to be randomized to treatment in a 2:1:1:1 ratio (72 subjects on placebo group and 37 subjects per intranasal esketamine dose group) to achieve 80% power to detect difference for at least one dose group of intranasal esketamine to placebo using a Dunnett adjustment. The treatment difference and SD used in this calculation were assumed based on results of Panel B of the ESKETINTRD2003 study with clinical consideration.¹⁶

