2.5. Definition of Subgroups

Analyses will be provided for the primary endpoint, changes from baseline in MADRS total score, using the following subgroups.

- Sex
- Age Group (<45 years, ≥45 years)
- Number of Previous Treatments in Current Episode
- Functional Impairment based on Baseline SDS Total Score (not impaired [0-3], mild [4-11], moderate [12-19], marked [20-26] or extreme [27-30])
- Baseline MADRS total score (≤/≥ Median)
- Class of oral antidepressant (SNRI, SSRI or mirtazapine)
- BMI (≤/≥ Median)
- Number of major depressive episodes including current episode (1, 2-3, 3<)
- Duration of the current episode (≤ 26, >26-52, >52-104, >104 weeks)
- Concomitant use of benzodiazepine excluding sleep aids (Y/N)
- Concomitant use of benzodiazepine including sleep aids (Y/N)
- Had been considered to be eligible for electroconvulsive therapy (Y/N)

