4.2.2. Primary Estimand

The primary estimand, the main clinical quantity of interest to be estimated in the study, is defined by the following 4 components:

Population: Japanese subjects with treatment-resistant depression

Variable: change from baseline to Day 28 in the MADRS total score (see Section 4.2.1)

Intervention effect: the effect of the initially randomized treatment that would have been observed had all subjects remained on their treatment throughout the double-blind induction phase.

Summary measure: difference in variable means.

The primary analysis will be based on the FAS (DB), as described in Section 2.4.2, and the MADRS total scores collected during the double-blind induction phase.

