4.2.3.1. MMRM

The primary efficacy variable, change from baseline in MADRS total score at Day 28 in the double-blind induction phase, will be analyzed using a Mixed-Effect Model for Repeated

Measures (MMRM) based on observed case data. The models will include baseline MADRS total score as a covariate, and treatment, day (see [Table 1](#)), and day-by-treatment interaction as fixed effects. The between-within approximation will be used to estimate the denominator degrees of freedom. The within-subject covariance between visits will be estimated via an unstructured variance-covariance matrix. In case of convergence problems, alternative variance-covariance structures will be tried in the following order, with the first structure that converges being used in the analysis: heterogeneous Toeplitz, standard Toeplitz, and AR(1) with separate subject random effect. Comparison of each esketamine dose group with the placebo group will be performed with the appropriate contrast using a Dunnett adjustment.

[figure not shown]
The change from baseline in MADRS total score over time in the double-blind induction phase will be analyzed using the same MMRM as described above.

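### Does the subgroup MMRM need a day-by-treatment-by-subgroup term before its Day 28 rows can be trusted?

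*SAP*

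**What the plan says.** SAP 4.2.3.5 says that the treatment difference and 90% interval for each subgroup "will be based on an MMRM analysis for the primary endpoint using the appropriate contrast". Besides baseline MADRS, the terms are "treatment, day, subgroup, day-by-treatment interaction and treatment-by-subgroup as fixed effects". For the baseline-MADRS subgroup the continuous covariate is dropped. Nothing else in the SAP adds a day-by-subgroup or three-way term.

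SAP 4.2.2 defines the primary variable as "change from baseline to Day 28 in the MADRS total score", so a row refers to Day 28. The primary model in SAP 4.2.3.1 has treatment, day "and day-by-treatment interaction as fixed effects", and takes its visits from Table 1 of SAP 2.3, which lists Days 2, 8, 15, 22 and 28 for the MADRS.

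SAP 2.5 names twelve subgroup factors. Seven have two levels. Four have three to five levels, and one ("Number of Previous Treatments in Current Episode") has no levels given. Under SAP 4.1.1 only the primary Dunnett comparisons are adjusted for multiplicity; everything else is nominal.

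**The concern.** The primary model lets the treatment effect differ by visit. The subgroup model keeps that for the overall effect but ties the subgroup's departure from it to one value for all visits. A row is therefore the Day 28 treatment effect plus a subgroup deviation averaged over visits, with weights set by the inverse covariance matrix. Early visits can carry much of that weight.

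If a subgroup difference grows over the phase, the Day 28 rows are drawn together. If it fades, they are pushed apart and the plot shows a difference that no longer exists at Day 28. In both cases the intervals cover less often than 90%. A reader of the plot would not see the assumption. At stake is how the subgroup plots are read.

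**Working it through.** **The plan's own figure.** Protocol 11.2 assumes effects of "4, 4.5, 5 points in MADRS total score between each dose" and placebo, SD 10, one-sided 0.05, 12.5% dropout, and 72 + 3 × 37 = 183 randomised. With 72 × 0.875 = 63 and 37 × 0.875 ≈ 32.4 evaluable, the Dunnett critical value is 2.106 and the power for at least one dose is 79.0%, close to the stated 80%. The subgroup model does not enter this calculation.

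**Assumed inputs.** The documents give no visit correlations, no visit-by-visit SDs for this design and no subgroup shares. The small IV study in Protocol 1.1.2.2 gives Day 2 SDs of 4.72 (placebo), 10.12 and 9.45, but these are too few data to build on. Fifteen settings were used: SD 10 throughout, rising 8 to 10, or rising 7 to 10, each with correlation 0.95, 0.97 or 0.98 per day apart, or compound symmetry 0.5 or 0.7. Because Day 2 uses a 24-hour recall (Protocol 9.2.1.2.1), while Protocol 9.2.1.1.1 assigns the 7-day recall to the primary evaluation, results are given with and without Day 2.

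**Formulas.** Let Σ be the visit covariance, S28 its Day 28 variance, f the subgroup share and δ the difference between the two subgroup levels by visit.

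- Weights w = Σ⁻¹1 / (1′Σ⁻¹1), and v = 1 / (1′Σ⁻¹1)
- c = 1/32.375 + 1/63 = 0.04676
- Row bias under the plan = (1 − f)(δ28 − w′δ)
- Row variance: plan c[S28 + v(1 − f)/f]; three-way model c·S28/f, with no bias

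**One setting in full.** SD 10, compound symmetry 0.5, no Day 2, f = 0.5, δ = 1, 2, 3, 4.

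- Each weight is 1/4, and v = 100 × (1 + 3 × 0.5)/4 = 62.5.
- Displayed difference: (1 + 2 + 3 + 4)/4 = 2.5 instead of 4. Row bias: 0.5 × (4 − 2.5) = 0.75.
- Plan variance: 0.04676 × 162.5 = 7.60, SE 2.76. Three-way variance: 0.04676 × 200 = 9.35, SE 3.06.
- Coverage under the plan: 0.75/2.76 = 0.272, so Φ(1.645 − 0.272) − Φ(−1.645 − 0.272) = 0.887.
- Root mean squared error (RMSE): plan √(0.75² + 7.60) = 2.86; three-way 3.06. The plan is closer to the truth on average despite its bias.
- Break-even: bias per point of Day 28 difference is 0.75/4 = 0.1875, so √(9.35 − 7.60)/0.1875 ≈ 7.1 points.

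**All 15 settings, 50/50 factor.** The RMSE of a three-way row is 3.06 in every setting.

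| Subgroup difference over Days 2, 8, 15, 22, 28 | Day 2 in model | Plan coverage | Plan has lower RMSE |
|---|---|---|---|
| Grows 0, 1, 2, 3, 4 | no | 86-89% | 15 of 15 |
| Grows 0, 1, 2, 3, 4 | yes | 80-88% | 10 of 15 |
| Grows evenly to 2 | no | 89.0-89.7% | 15 of 15 |
| Grows evenly to 2 | yes | 87.4-89.5% | 15 of 15 |
| Early onset, plateau: 2, 3, 3.5, 4, 4 | no | 89.6-89.9% | 15 of 15 |
| Early onset, plateau: 2, 3, 3.5, 4, 4 | yes | 88.0-89.7% | 15 of 15 |
| Constant | either | 90% | 15 of 15 |

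For the growing shape, the break-even Day 28 difference is 4.3-7.1 points without Day 2 and 3.2-5.5 with it. The whole planned drug effect is 4 to 5 points.

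**Simulation check.** With 700 runs, 84 mg, no Day 2, SDs 8 to 10 and correlation 0.97 per day, a 4-point difference growing from nothing gives true rows of −7.0 and −3.0. The plan gave −6.1 and −4.1 (coverage 88% and 88%, RMSE 2.9 and 2.9). The three-way model gave −7.2 and −2.9 (90% and 90%, RMSE 3.0 and 3.0). The Monte Carlo SE of coverage is 1.1 points.

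**Price of the extra term.** Rows for a 50/50 factor widen by 4-17% without Day 2 and 6-20% with it. The smaller row of a 30/70 factor widens by up to 27% or 33%, and rests on about 0.3 × 37 ≈ 11 randomised per active arm. A two-level factor needs 2 × 4 arms × 4 visits = 32 means. Five levels need 80, with about 37/5 ≈ 7 randomised per active arm per level. The term is therefore practical for only seven of the twelve factors.

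**The case for a change.** The strongest case on the other side is that a row presented for Day 28 should estimate Day 28 with its nominal coverage, whatever its total error. With Day 2 in the model and SDs rising from 7 to 10, the worst of the 15 settings shows a true 4-point growing difference as about −0.1, with 80% coverage. A difference fading from 4 to 0 is shown as 2.0-4.1 points. Smaller subgroups fare worse: for a 25% level, the growing 4-point case gives coverage of 86.4% down to 74.3%.

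There is also a reason to look at baseline severity. Protocol 1.1.2.2 reports a treatment-by-baseline-MADRS interaction (p = 0.052) in the Japanese panel of the earlier study after one week. The planned model would carry such an early effect into the Day 28 row.

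The arithmetic stands. What it lacks is evidence that the damaging pattern occurs. The one-week interaction does not show a subgroup effect changing over visits. The 28 mg result in the same section, "with the MADRS total score higher on Day 8 than on Day 2", is a treatment-by-time pattern, which the planned day-by-treatment term already handles. The low coverage figures need a large difference that starts at nothing or ends at nothing, and the lowest also need Day 2 in the model and early SDs well below the final one. It is fair that the SAP does not state the constancy assumption. A plot label saying so would help a reader but would change no estimate.

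**Conclusion.** The concern does not hold as an error in the plan. SAP 4.2.3.5 does assume a subgroup deviation that is constant over visits, and a changing deviation would bias the Day 28 rows. But pooling a small-sample subgroup effect over visits is an ordinary bias-variance choice. For a 4-point difference growing from nothing, the plan has the lower RMSE in 15 of 15 settings without Day 2 and 10 of 15 with it. For milder or earlier-onset patterns it is better throughout, and for a constant effect it is both unbiased and more precise. The alternative costs 4-20% in interval width for an evenly split factor and cannot sensibly be applied to five of the twelve factors.

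The primary MMRM, the Dunnett test, alpha and N = 183 are untouched, and the rows carry no confirmatory claim. The conclusion rests on the assumed covariances and profiles above. It would weaken if there were grounds to expect a Day 28 subgroup difference beyond the break-even values that had grown from near zero, or an early difference of that size that fades away. The documents give no such grounds.

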4.3. Secondary Endpoints

4.3.1. Responders

4.3.1.1. Definition

The percentage change from baseline at Day X is calculated as $100 * (\text{MADRS total score at Day X} - \text{Baseline MADRS total score}) / (\text{Baseline MADRS total score})$. Negative percent changes in MADRS total score indicate improvement (eg, percent change $\leq -50\%$ indicates improvement $\geq 50\%$). For the open-label induction phase, OL baseline will be used to calculate the percentage change as well.

A subject is defined a responder (yes=1 and no=0) at a given time point if the percent improvement in MADRS total score is $\geq 50\%$.

4.3.1.2. Analysis Methods

The proportion of subjects who achieve a response will be summarized at each time point for each induction phase (DB and OL). The proportion of responders during the double-blind induction phase in the esketamine dose group will be compared with the placebo group using Fisher's exact test with 90% CIs for the proportion provided by treatment group.

The cumulative response rate, defined as the percentage of subjects experiencing at least a given value of percent reduction from baseline to Day 28 in MADRS total score will be presented graphically.

The cumulative distribution function of the time to sustained response will be estimated by the Kaplan-Meier method for double-blind induction phase. Time to sustained response will be summarized (number of sustained responders, number of censored subjects, median, 25th and 75th percentile, if estimable) by treatment group. Sustained response is defined as the first occurrence of response that is maintained through the Day 28 assessment. Subjects are allowed one excursion (nonresponse) on a subsequent visit prior to Day 28, however the score must show at least 25% improvement. Subjects who discontinue early are not considered to have sustained response. Those subjects without sustained response will be censored at the last visit during double blind induction phase.

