Visit number	1.1 ^b	2.1 ^b	2.2	2.3	3.1 ^a	3.2	3.3	3.4	3.5	3.6	3.7	3.8	3.9	3.10 ^m	EW ^c	
Study Week	Within 4 weeks of Day P1	-6	-4	-2	1			2		3		4			—	
Study day	-70 (P-28 to P-1)	-42 (P1)	-28 (P15)	-14 (P29)	1 (P43) Prerandomization Postrandomization		2	4	8	11	15	18	22	25	28	EW
Clinic visit window (days)		-3	±3	±3	—	—	—	±1	±1	±1	±1	±1	±1	±1	±1	—
Remote MADRS interview window (in days; relative to Study day [not including visit window])		-3	±3	±3	—	—	—	—	-2 ^d	—	-2 ^d	—	-2 ^d	—	-2 ^{d,p}	—
Clinic visit (C) or remote MADRS interview only (RM)		C	C	C	C		RM	C	C	C	C	C	C	C	C	C
Ongoing Subject Review																
Concomitant therapy	X	X	X	X	X	X		X	X	X	X	X	X	X	X	X
Adverse events	X	X	X	X	X	X		X	X	X	X	X	X	X	X	X

Footnotes:

Note: On intranasal dosing days, time 0 is defined as the time of the first intranasal spray. Therefore, postdose time points are referenced from this.

- Visit 3.1 Prerandomization must coincide exactly on the same day as Visit 3.1 Postrandomization. All subjects who will be randomized and enrolled in the double-blind induction phase must meet all of the inclusion criteria and none of the exclusion criteria at Visit 3.1 Prerandomization. After randomization, all subjects will proceed to Visit 3.1 Postrandomization.
- If clinically indicated, cross tapering is allowed.
- If a subject withdraws before the end of the double-blind induction phase (ie, before completing Visit 3.10/Day 28) for reasons other than withdrawal of consent, an EW Visit should be conducted within 1 week of the date of discontinuation, followed by the follow-up phase. If the EW Visit is conducted on the same day as a scheduled visit, duplicate assessments are not required.
- MADRS assessment should be conducted at predose.
- Predose (if/when performed on intranasal dosing days). With the exception of postdose assessments, subject-reported outcome assessments should be administered before all other study-related procedures during a clinic visit.
- Postdose vital signs will be performed at 40 minutes, 1 hour, and 1.5 hours postdose. Please refer to Section 6.3.1 for guidance for blood pressure monitoring on intranasal dosing days.

-
- g. Twelve-lead ECG will be performed at $t=1$ hour postdose at Visit 3.1 Postrandomization. Twelve-lead ECG will be performed at $t=1$ hour postdose at Visits 3.4 to 3.9 (only at the time points indicated), but no predose ECGs are required at Visits 3.4 to 3.9. A time window of ± 15 minutes is permitted.

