2.1.2. Analysis Phase Start and End Dates

Double-blind Induction Phase

The start date of the double-blind induction phase (referred to as ‘DB start date’) is the date of the first dose of intranasal study medication. The double-blind induction phase end date (referred to as ‘DB end date’) is the maximum of the date of the last visit in the double-blind induction phase and the date of completion/withdrawal from the double-blind induction phase.

The start date/time of the double-blind induction phase (referred to as, ‘DB start date/time’) is the DB start date and the time of the first dose of intranasal study medication.

Double-blind Follow-up Phase

The start date of the double-blind follow-up phase (referred to as ‘DB FU start date’) is the day after the DB end date. The double-blind follow-up phase end date (referred to as ‘DB FU end date’) is the maximum of the last DB follow-up visit date or the end of trial date.

Posttreatment Phase

The start date of the posttreatment phase (referred to as ‘PT start date’) is the day after the DB end date. The posttreatment phase end date (referred to as ‘PT end date’) is defined as: for subjects who entered OL phase, the day of OL start date (defined below); for subjects who did not enter OL, including responders who withdraw within 4 weeks after the last dose of DB intranasal drug, the maximum of the last posttreatment visit date or the end of trial date.

For subjects who entered OL phase, PT end date/time is one minute before OL start date/time (defined below).

Open-Label Induction Phase

The start date of the open-label induction phase (referred to as ‘OL start date’) is the date of the first dose of intranasal study medication in a second induction treatment course. The open-label induction phase end date (referred to as ‘OL end date’) is the maximum of the date of the last visit in the open-label induction phase and the date of completion/withdrawal from the open-label induction phase.

The start date/time of the open-label induction phase (referred to as, ‘OL start date/time’) is the OL start date and the time of the first dose of intranasal study medication in the second induction treatment course.

Open-Label Follow-up Phase

The start date of the open-label follow-up phase (referred to as ‘OL FU start date’) is the day after the OL end date. The open-label follow-up phase end date (referred to as ‘OL FU end date’) is the maximum of the last OL follow-up visit date or the end of trial date.

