4.1.2. Data Handling Rules

As a sensitivity analysis, the change in MADRS total score will be analyzed using an analysis of covariance (ANCOVA) model, using last observation carried forward (LOCF) data. The last post baseline observation during the double-blind induction phase will be carried forward as the “End Point” for that phase. Besides the observed cases and the end point assessment, the LOCF values will be created for intermediate postbaseline time points as well. These imputed time points will be labeled ‘DAY X LOCF’.

For the analyses of responders based on MADRS total score (Section 4.3.1), remitters based on MADRS total score (Section 4.3.2), subjects with missing values will be imputed as nonresponders/nonremitters.

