4.3.2.2. Analysis Methods

The proportion of subjects who achieve remission will be summarized at each time point for each induction phase (DB and OL). The proportion of remitters during the double-blind induction phase in the esketamine dose group will be compared with the placebo group using Fisher's exact test with 90% CIs for the proportion provided by treatment group.

The cumulative distribution function of the time to sustained remission will be estimated by the Kaplan-Meier method for double-blind induction phase. Time to sustained remission will be summarized (number of sustained remitters, number of censored subjects, median, 25th and 75th percentile, if estimable) by treatment group. Sustained remission is defined as the first occurrence of remission that is maintained through the Day 28 assessment. Subjects are allowed one excursion (MADRS total score >12) on a subsequent visit prior to Day 28. Subjects who discontinue early are not considered to have sustained remission. Those subjects without sustained remission will be censored at the last visit during double-blind induction phase.

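### Kaplan-Meier curves for time to sustained response and remission censor early discontinuers whom the SAP already counts as failures, so they can overstate the Day 28 proportion

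*SAP*

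**What the plan says.** SAP 4.3.1.2 estimates the distribution of time to sustained response in the double-blind phase by Kaplan-Meier, by treatment group. The event is the first response that then holds to the Day 28 assessment, with one limited excursion allowed. Two sentences follow. The first says "Subjects who discontinue early are not considered to have sustained response". The second says "Those subjects without sustained response will be censored at the last visit during double blind induction phase". The table is to show "number of sustained responders, number of censored subjects, median, 25th and 75th percentile, if estimable".

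SAP 4.3.2.2 repeats the pattern for remission: "Subjects who discontinue early are not considered to have sustained remission", then "Those subjects without sustained remission will be censored at the last visit during double-blind induction phase".

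Three other places bear on the point.

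- **Failure rule for proportions.** For the responder and remitter proportions, SAP 4.1.2 states that "subjects with missing values will be imputed as nonresponders/nonremitters". SAP 4.3.4.1 likewise assigns 0 to anyone who leaves before Day 28 in the onset-of-response analysis.
- **Date of the last visit.** For a discontinuer who has not withdrawn consent, footnote c of the protocol's Time and Events Schedule 1 says "an EW Visit should be conducted within 1 week of the date of discontinuation". SAP 2.1.2 ends the double-blind phase at "the maximum of the date of the last visit in the double-blind induction phase and the date of completion/withdrawal". The censoring visit can therefore be an Early Withdrawal (EW) visit.
- **Day 28 window.** SAP 2.3, Table 1 places any MADRS from Day 26 to the end of the phase in the Day 28 window.

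**The concern.** Sustained response requires response up to Day 28, so under the SAP's definition a subject who leaves early cannot have the event. That subject's status is known. Censoring removes the subject from the risk set as if it were unknown, and the product-limit estimator then assigns the subject the later event probability of those who remained. The curve no longer estimates the proportion of the arm with sustained response, which the definition describes and the reported count represents.

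Three things are at stake in how the output is read:

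- The Day 28 height of the curve can disagree with the number of sustained responders printed beside it, divided by N.
- A quartile can appear earlier, or appear as estimable when fewer than the required fraction of the arm had the event.
- The excess grows with an arm's dropout, so of two arms with the same success count, the one losing more subjects can look better. Protocol 3.2.4 expects some intolerability discontinuation at 84 mg, so dropout could differ by dose.

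**Working it through.** **Inputs.** From Protocol 11.2 and SAP 1.4: 72 placebo subjects, 37 per esketamine dose, 12.5% dropout. These agree with each other: 63/0.875 = 72; 32/0.875 = 36.6, rounded up to 37; 72 + 3 × 37 = 183. The MADRS visits are Days 2, 8, 15, 22 and 28. Dropouts per arm: 0.125 × 37 = 4.6, taken as 5; 0.125 × 72 = 9. The plan gives no expected figure for these curves, no sustained-response rate and no dropout by arm. **All event counts and timings below are assumptions.**

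**Bound.** Let p be sustained responders divided by N, and d the dropout fraction. If no event follows a censoring, 1-KM at Day 28 equals p. If every dropout is censored before the first event, it equals p/(1 − d). The excess therefore lies between 0 and p·d/(1 − d). At d = 0.125 the relative ceiling is 0.125/0.875 = 14.3%. With whole subjects, 5 of 37 is 13.5% dropout, so in the example below the ceiling is 5/32 = 15.6% relative, that is 18/32 = 56.3% against 18/37 = 48.6%.

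**Esketamine arm, n = 37.** Events 3, 5, 4, 3, 3 at the five visits (18 in total), 5 dropouts, events counted before censoring at ties.

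- *Dropouts spread 2, 1, 1, 1, censored at Days 2, 8, 15, 22.* Survival = 34/37 × 27/32 × 22/26 × 18/21 × 14/17 = 0.463, so 1-KM = 53.7%.
- *Same spread, each censoring one visit later because of EW visits.* 34/37 × 29/34 × 23/27 × 19/22 × 15/18 = 0.481, so 1-KM = 52.0%.

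| When the 5 dropouts leave | 1-KM, censored at the last visit before dropout | 1-KM, one visit later (EW) |
|---|---|---|
| all after Day 2 | 55.6% | 54.3% |
| spread 2, 1, 1, 1 | 53.7% | 52.0% |
| all after Day 22 | 51.0% | 48.6% (no excess) |
| crude, 18/37 | 48.6% | 48.6% |

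Every value above 50% yields a reported median although 18 of 37 is fewer than half. The last EW cell shows no excess because censoring then falls at Day 28.

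**Placebo arm, n = 72.** Events 3, 7, 6, 5, 4 (25 in total; crude 25/72 = 34.7%), 9 dropouts spread 3, 2, 2, 2. Survival = 69/72 × 59/66 × 51/57 × 44/49 × 38/42 = 0.623, so 1-KM = 37.7%. One visit later it is 36.6%.

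**Unequal dropout.** Take two arms of 40, each with 12 events (30.0%), 3 at each of Days 8, 15, 22 and 28. With 2 dropouts (one censored at Day 8, one at Day 15), survival = 37/40 × 33/36 × 29/32 × 26/29, so 1-KM = 31.1%. With 8 dropouts (2, 3, 3 at Days 2, 8, 15), survival = 35/38 × 29/32 × 23/26 × 20/23, so 1-KM = 35.8%. The success counts are equal and the curves are 4.7 points apart.

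**Quartiles.** Event totals from 4 to 25 of 37 (22 totals) were run under four assumed event-timing profiles with 5 spread dropouts. At least one quartile differs from the crude one in 7 to 10 of 22 totals, depending on profile. With the one-visit EW delay, the range is 3 to 6 of 22.

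**Check of the remedy.** With all non-events censored at nominal Day 28, the first example gives 3/37, 8/37, 12/37, 15/37 and 18/37 (8.1, 21.6, 32.4, 40.5, 48.6%), whatever the dropout timing. The Aalen-Johansen estimate with discontinuation as a competing event gives the same five values.

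**The case against.** The strongest defence is that the two sentences are sequential. The first only stops someone who responds on Day 8 and leaves on Day 15 from counting as an event at Day 8; the second then supplies a censoring time. On that reading the curve targets what would have happened had nobody left, which matches the hypothetical estimand of SAP 4.2.2. The missing-as-failure rule of SAP 4.1.2 is written for the responder and remitter proportions and does not name these curves.

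This does not rescue the text as written. SAP 4.2.2 defines the estimand for the primary MADRS change only, nothing in 4.3.1.2 or 4.3.2.2 invokes it, and both sections define the outcome so that leaving early is a failure. If the hypothetical reading is meant, the SAP has to say so.

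Other parts of the defence do stand. A reader can divide the reported count by N. The proportions with missing counted as failure are reported separately, and nothing tested depends on these curves. The 18-of-37 example is the highest count below half, chosen to show the median effect. EW visits shrink the excess and can remove it for late dropouts. In most of the scanned scenarios no quartile changes.

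**Conclusion.** The concern holds: the censoring rule conflicts with the event definition in the same paragraph, in both sections. The curve overstates the Day 28 proportion whenever an event follows a discontinuer's last double-blind visit, and is exact otherwise. At 12.5% dropout the excess is at most 14.3% relative. In the assumed spread-dropout examples it is 5.0 points in a 37-subject arm (3.3 with EW delay) and 3.0 points in the placebo arm (1.9 with EW delay). The direction and the bound follow from the SAP's own rules on nominal visit time; the particular sizes rest on assumed event counts and timings.

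The point is minor. The outputs are descriptive, carry no test, and are not among the 12 secondary endpoints of Protocol 9.2.2.2. The primary MMRM and the Fisher tests are untouched.

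**What to change.** Replace the censoring sentence in SAP 4.3.1.2 and 4.3.2.2 with: *Time will be measured in nominal analysis-visit days. Subjects without sustained response (remission), including those who discontinue early, will be censored at nominal Day 28, with events at Day 28 counted before censoring.* The nominal scale matters because, on actual days, completers without the event who are assessed on Day 26 or 27 would also be censored before later events.

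A cumulative incidence function with discontinuation as a competing event is an equivalent alternative. If the hypothetical reading is intended, keep the present rule, state that estimand in both sections and label the curve accordingly.

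The cost is one sentence in each of two sections and one derivation line, with no new data. The descriptive percentages become slightly less favourable.
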